3. STUDY DESIGN

The **SchistoSAM** study is an open label, two-arm, individually-randomized controlled trial among infected primary school-age children in northern Senegal, with a non-inferiority design.

The study will take place during the rainy season (July-October) to maximize the potential benefits of repeated AM administrations on both schistosomiasis and malaria.

At baseline, prior to the first drug administration, all children fulfilling the study criteria (chapter 4.2) will undergo a full parasitological and morbidity assessment of:

- schistosomiasis infection: by microscopy (stool Kato-Katz and urine filtration) and point-of-care assays on site (POC-CCA) as well as additional diagnostics on preserved urine/stool samples (a UCP-LF CAA assay and a real time stool and urine PCR)
- 2. schistosomiasis systemic and organ-specific morbidity: by clinical evaluation, ultrasound, point-ofcare morbidity markers and hemoglobin level
- 3. malaria infection: by determination of prevalence through molecular testing on preserved blood samples, and prevalence/pattern of molecular markers of resistance
- 4. malaria morbidity: by measurement of proportion and severity of anemia

Subsequently, children will be randomized and assigned to one of the two following study arms:

- 5. **AM arm**: Three-day course of AM (A: 4 mg/kg and M: 8 mg/kg per day, given once a day for three days) administered at baseline and repeated twice at 6-week intervals (intervention).
- 6. **PZQ arm**: Single dose of PZQ (40 mg/kg) administered at study inclusion (control arm/standard of care).

The 6-weeks interval between AM administrations corresponds to the time lapse for larval maturation (from infection to adult worms). In addition, this 6-week period should minimize/prevent the risk of cumulative mefloquine-associated toxicity.

[figure not shown]
Parasitological assessments of schistosomiasis (urine and stool microscopy and POC-CAA) will take place in both arms at week 4, 10 and 16 after first administration of AM or PZQ. Full parasitological assessment of schistosomiasis and malaria (urine, stool and blood analysis) will be repeated at week 24 and 48 post-inclusion.

Morbidity assessment will be repeated as described here above at week 24 and 48 after initial treatment. These assessments are described in more detail in chapter 5.

At week 48 post-inclusion, the children of both arms will receive a dose of PZQ. National control programs will be informed the study outcomes, including on the prevalence of schistosomiasis infection, to assist them in the organization of mass drug administration for non-study participants. This MDA will be coordinated by the national control program according to guidelines in force in Senegal. ^{74,75}

Also, children in the study testing positive for schistosomiasis by microscopy or POC-CCA at baseline, but who cannot participate to the study, will be treated with PZQ and, if needed, referred to health facilities for further care.

Figure 1: Study flowchart

There will be no blinding of the investigators nor participants because of the practical difficulty and costs to get a double dummy, since the intervention regimen is very different from the control arm. However, the results of the successive parasitological assessments will be masked to the clinical teams in the study sites, so that their evaluation of drug safety and tolerability will not be influenced if the efficacy data appear favorable. Similarly, the laboratory study team will be blinded for the treatment arm allocation.

Adverse events up to four weeks after the last dose of study medication (PZQ or AM) will be carefully monitored and SAEs will be immediately reported to the principal investigator, the project coordinator and the Data and Safety Monitoring Board (DSMB) (see chapter 7 for more details on safety reporting). Before each additional AM administration, the DSMB will receive by mail a list of the frequency, pattern and severity of AEs observed in both treatment arms, to be able to react accordingly.

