2.2. Secondary objectives

1. To evaluate the safety and cumulative efficacy of two additional courses of AM (at 6-week intervals each) for the treatment of schistosomiasis, compared to a single course of AM, and compared to the standard PZQ regimen (control arm).

Endpoint measures:

- Efficacy: CR, as assessed by microscopy, after the second and after the third AM administration (at week 10 and 16, 24 and 48 see study flowchart),
- Safety: Frequency and pattern of AEs and SAEs up to 4 weeks after the second and third AM administration.
- 2. To determine the egg reduction rate (ERR) obtained after single and repeated courses of AM compared to the standard PZQ regimen.
 - Endpoint measure: ERR after administration of PZQ and after each AM course (at week 4, 10, 16, 24 and 48 see study flowchart).
- 3. To determine the parasitological efficacy of single and repeated courses of AM by *Schistosoma* species and by infection intensity.

Endpoint measures: CR and ERR by initial *Schistosoma* infection intensity after PZQ administration and single and repeated courses of AM. (measured at week 4, 10 and 16 after first AM administration)

- 4. To assess the impact of repeated AM courses on schistosomiasis-related morbidity. Endpoint measures: Prevalence and severity of general and organ-specific schistosomiasis morbidity (as assessed by clinical evaluation, ultrasound, point-of-care morbidity markers and hemoglobin level) at week 24 and week 48 compared to baseline and compared to the control arm.
- To determine the diagnostic performance of novel schistosomiasis antigen- and DNA-based diagnostic assays to monitor antischistosomal treatment response.
 Endpoint measures: Sensitivity and specificity of the different conventional and novel diagnostic tests at baseline and at defined time points after treatment compared to conventional microscopy, and to composite reference standards.

6. To determine the effect of repeated AM courses on prevalence of *P. falciparum* infection as well as on incidence and morbidity of clinical malaria in school-age children with schistosomiasis.

Endpoint measures:

- Prevalence of malaria infection, as assessed by molecular testing of dried blood spots at baseline and week 24 and 48.
- Incidence of clinical malaria, as assessed by the number of incident malaria cases diagnosed through passive case detection during the study period (by standard malaria rapid tests and molecular diagnostics on dried blood spots).

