4.4. Randomization

A block randomization schedule - to ensure balance of the two arms among the study sample, stratified for the two species of Schistosomiasis, will be prepared by the sponsor biostatistician. The individual randomization number and treatment arm of each subject will be stored in sealed envelopes.

Randomization will be done at the time of enrollment using randomization envelopes, specifying the treatment arm. This is an open-label study, so both the study team members as well as the participant will immediately be informed about the assignment to one of the two study arms. The randomization list will be prepared using SAS 9.4 (SAS Institute, Cary NC).

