A suitable place will be prepared on site for ultrasound examinations and they will be all performed by a qualified person, following the scores from the WHO guidelines ⁷⁹.

Study specific SOPs will be developed with detailed guidance for site staff on how to perform the above-mentioned study procedures.

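### No provision masks the examiners who score ultrasound and physical examination at weeks 24 and 48 to treatment arm, leaving avoidable assessor bias in two components of secondary objective 4

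*Protocol*

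**What the plan says.** **Masking.** Protocol section 3 states: "There will be no blinding of the investigators nor participants because of the practical difficulty and costs to get a double dummy". Two partial measures follow. First, "the results of the successive parasitological assessments will be masked to the clinical teams in the study sites"; the stated purpose is to keep the evaluation of safety and tolerability free of influence from efficacy data. Second, "the laboratory study team will be blinded for the treatment arm allocation". Section 4.4 adds that "both the study team members as well as the participant will immediately be informed about the assignment to one of the two study arms".

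**Endpoint.** Secondary objective 4 (section 2.2) is "Prevalence and severity of general and organ-specific schistosomiasis morbidity (as assessed by clinical evaluation, ultrasound, point-of-care morbidity markers and" hemoglobin level, assessed "at week 24 and week 48 compared to baseline and compared to the control arm".

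**Who examines.** Section 5.1 names a radiologist with experience of schistosomiasis for the ultrasound at recruitment. Section 5.3 says of the ultrasound examinations that "they will be all performed by a qualified person, following the scores from the WHO guidelines". The same section describes clinical examination, drug administration and ultrasound together, as on-site tasks of experienced health staff. Neither section mentions masking of the examiner.

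**The concern.** Ultrasound lesion scores, and liver and spleen size judged by palpation, depend on the examiner. An examiner who knows the arm may, without intending to, read a borderline periportal, bladder-wall or spleen finding differently in the two arms. The trial's hypothesis is directional, since repeated artesunate-mefloquine is expected to do better than praziquantel, so there is an expectation to act on. A between-arm difference in these findings at week 24 or 48 could then not be separated from reader expectation. No later analysis can restore masking that was absent when the scan was scored.

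**Working it through.** The plan gives no figure for this point, so the check sets the provisions side by side.

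**Step 1. Who is masked to what.**

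| Group | Masked to arm? | Masked to egg results? | Source |
|---|---|---|---|
| Participants and investigators | No | Not stated for participants; site clinical teams yes | Section 3 |
| Study team members | No, told at randomization | Site clinical teams yes | Sections 3, 4.4 |
| Laboratory team | Yes | Not applicable, it produces them | Section 3 |
| Ultrasound examiner | No provision | Only if counted in the clinical team | Sections 3, 5.1, 5.3 |
| Clinician examining at weeks 24 and 48 | No provision | Yes | Sections 3, 5.1, 5.3 |

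Masking clinical teams to egg results does not mask them to allocation.

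**Step 2. Which parts of objective 4 are exposed.**

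| Component | How obtained | Exposed? |
|---|---|---|
| Ultrasound | Scored on site by an examiner (5.3) | Yes |
| Physical examination | Palpation and observation (5.3) | Yes |
| Hemoglobin | Portable hemoglobinometer (5.3) | Little scope, instrument reading |
| Urine strip, fecal occult blood | Listed under laboratory procedures (5.4.1) | Not on the natural reading, as the laboratory is masked; the reader is not named |

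The primary efficacy endpoint, the week-4 cure rate by microscopy (sections 2.1 and 5.4.1), falls under the laboratory masking.

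**Step 3. Baseline against follow-up.** Sections 3 and 5.1 place the recruitment ultrasound before randomization, so the baseline score cannot reflect knowledge of the arm. The scores at weeks 24 and 48 can. A shift at follow-up would therefore enter both the comparison between arms and the change from baseline.

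**Step 4. Whether the stated reason covers the gap.** The only reason given for open label is the practical difficulty and cost of a double dummy. A dummy is needed to mask the child and the person giving the drug. It is not needed to keep the arm from someone who only scans. The protocol already accepts this for the laboratory.

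**Step 5. Size.** Let *p* be the true lesion prevalence, equal in both arms, and *f* the share of lesion-free children wrongly scored positive in one arm only. The spurious difference is (1 − *p*) × *f*. The protocol gives neither quantity. With assumed *p* of 5% to 30%:

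- *f* = 2%: from 0.70 × 2% = 1.4 points to 0.95 × 2% = 1.9 points.
- *f* = 5%: from 0.70 × 5% = 3.5 points to 0.95 × 5% = 4.75 points.

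The result is essentially the assumed *f* carried through. It shows how the bias would arise and is not an estimate of it.

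**The case against.** The case for leaving the text alone has several parts.

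- **The gap is inferred from silence.** No sentence says the ultrasound examiner is told the arm, and section 5.3 defers procedures to SOPs still to be written. This is true, and those SOPs could add masking. But section 3 deals with masking expressly and names only the laboratory as masked to allocation, while section 4.4 tells study team members the arm. Followed as written, nothing prevents the examiner from knowing it. Because this is a design provision, it is not detail that can be left to the statistical analysis plan.
- **WHO scoring limits discretion.** It does, but standard scores do not settle borderline readings.
- **Forms already carry only a study code.** Sections 10, 11.4 and 11.6.1 require coded records. Those clauses protect confidentiality and do not say that the arm is kept off the page.
- **Separating roles has a cost.** Section 5.3 describes dosing and ultrasound together, and no staffing figures are given, so some change of roster may be needed. This stands and is named under the fix.

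A reader might also infer more than the protocol supports:

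- That nobody who scores morbidity is masked. The tests listed as laboratory procedures naturally fall under the laboratory masking.
- That examiners will know the week-16 results. Section 8.3.6 says the interim efficacy results will be communicated but not to whom, and section 3 masks parasitological results to the site clinical teams. Such knowledge is speculation.
- That masking the examiner would remove the bias. Children know their arm and may say so.
- That a shift of some 3 to 5 percentage points is to be expected. Such a figure only repeats an assumed reclassification rate.

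**Conclusion.** The point holds for two components of one secondary objective: ultrasound and physical examination at weeks 24 and 48. Both depend on the examiner, both are compared between open-label arms, and no provision masks the examiner to allocation. The stated reason for open label does not cover this. The conclusion rests on reading sections 3 and 4.4 as they stand and on the absence of any masking statement for these examiners.

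The size of the bias cannot be estimated from the protocol. The primary week-4 cure rate, the non-inferiority conclusion and the sample size do not depend on it. This is a worthwhile, inexpensive improvement to a secondary comparison and does not threaten the trial's main result.

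**What to change.** Add to sections 3 and 5.3, and carry into the ultrasound SOP:

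> The ultrasound examiner at weeks 24 and 48 is not told the treatment arm and takes no part in study drug administration. The ultrasound worksheet and eCRF page do not show the arm. Where the existing roster allows, the same applies to the clinician who performs the morbidity examination at these visits.

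The cost is a short protocol amendment, a check that the arm does not appear on the worksheet and eCRF page, and some separation of roles on the roster. No double dummy and no additional reader of the scans is required. Masking will be partial, because children may disclose their arm, so bias is reduced and not eliminated. The change must be in place before the week-24 scans.

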4. PARTICIPANTS, POPULATION & SELECTION

4.1. Settings, selection & recruitment of the study population

The trial will be conducted in the northern region of Senegal, in the commune of Richard Toll located in the department of Dagana and the Saint-Louis region. Schistosomiasis in this region is highly endemic with mixed *Sm* and *Sh* infections and reported prevalence of >50% in the general population and up to 80% in school-age children ⁷⁶. Malaria transmission is seasonal and very low (annual incidence < 5/1,000 inhabitants) in this region, when assessed by light microscopy or rapid diagnostic test. Prevalence of Pf infection was rather low (1%) with more sensitive molecular assays in a neighboring northeastern area ⁷⁶, although substantially higher (up to 15%) in neighboring southwestern regions ⁷⁷. The rainy season lasts usually from June to October in this region. This area with high prevalence and incidence of both *Schistosoma* species (and very low incidence of malaria) is then considered as particularly suited to safely test a "new" antimalarial drug with dual activity in a proof-of-concept trial. Such a setting provides a unique opportunity to obtain very robust data on efficacy against schistosomiasis while minimizing the risk of malaria resistance (the latter being very unlikely since AM is a potent ACT). However, scrutinizing the effect of AM on *Pf* infection (including asymptomatic malaria) and resistance remains key in the project.⁷⁶.

The trial will be conducted by the "Institut de Recherche en Santé de Surveillance Épidémiologique et de Formation" (IRESSEF) with the support of ITM. IRESSEF - accredited ISO 15189/15190 - is a 'not-forprofit' public institution hosting the African Network for HIV Research (RARS) which includes 22 West and Central African countries. IRESSEF staff has long and strong experience in research on HIV, Tuberculosis, Malaria and Neglected Diseases. IRESSEF possesses resources and infrastructures to conduct technically demanding studies including units of malaria, clinical trial, epidemiology, data management, and IT. It has scientific and technical partnerships with prestigious universities such as Harvard, Oxford, Imperial College, as well as national institutions and universities including among other the Ministry of Health (with whom it has signed a partnership agreement) and the Cheikh Anta Diop University of Dakar. Since 2007 under LBV-UCAD, scientists from IRESSEF have collaborated with the ITM in various projects in the field of schistosomiasis in Northern Senegal (DGD/EU/SchistoINIR). IRESSEF is presently coordinating the second phase of the West African Network for TB, AIDS and Malaria (WANETAM2) - funded by EDCTP.

The commune of Richard Toll compasses about 37 primary schools in total, with a number of pupils ranging from 50 to more than 200 per school. Because schistosomiasis transmission is typically focal and evolving, the prevalence of schistosomiasis will be however re-assessed according to the WHO methodology. Schools will be selected according to their size, proximity to Richard Toll and prevalence of schistosomiasis. A list of priority schools will then be established, where selection and recruitment of children for the clinical trial will take place.

School directors and teaching staff will be informed during a preparatory visit, in close collaboration with the study teams. Specific information on the targeted disease (schistosomiasis and malaria) and the risk/benefits of the trial will then be shared in a culturally-sensitive way with local communities. They will have the possibility to ask questions. The members of the study team from IRESSEF in Senegal who have already established contact with local communities will facilitate this sharing of information. The parents/guardians of the school children will be invited for a general information session and an individual informed consent process (detailed informed consent procedure in chapter 5.2). Those that consent will give a stool and urine sample for identification of schistosomiasis infection.

Eligible children positive for schistosomiasis will then be invited to come for medical and initial parasitological and morbidity assessment, and enrolment in one of the two randomly assigned study arms. Children that tested positive for *Schistosomiasis* but are not eligible will be offered standard

treatment with PZQ. We will keep screening until we achieve the necessary 726 enrollments (363 in each arm; details of sample size in chapter 4.3).

4.2. Inclusion and exclusion criteria

Inclusion criteria

- 1. Children ≥ 6 and ≤ 14 years of age
- 2. Enrolled in one of the selected primary schools in the district of Richard Toll
- 3. Infected with schistosomiasis (i.e. presence of Schistosoma spp. eggs in urine and/or stool)
- 4. Informed consent from parents/guardians signed

Exclusion criteria

- 1. Planned travel of more than 1 months within the first 4 months after enrolment
- 2. History of, or ongoing, epilepsy or psychiatric illness (i.e. recent history of depression, generalized anxiety disorder; history of psychosis, schizophrenia or other major psychiatric disorders) or known hypersensitivity to one of the three study drugs
- 3. Chronic medication for any reason
- 4. Any severe underlying illness, including severe malnutrition or severe chronic schistosomiasis, based on clinical judgement
- 5. Any febrile illness or clinical malaria
- 6. Exposure to PZQ or ACT within the three previous months.

As mentioned above, children with schistosomiasis but excluded from the study will be treated with PZQ according to standard of care in Senegal. Children found with other illnesses or severe schistosomiasis will be referred to adequate health facilities for further care.

4.3. Sample size

The sample size was calculated on the parasitological cure rate endpoint after the first course of AM, to test the hypothesis that AM is non-inferior to PZQ: at least a 65% cure rate with AM as compared to a 75% cure rate with PZQ according to the following rationale. We consider that a cure rate (CR) of 65% is clinically acceptable as threshold for non-inferiority for the AM combination, for the following reasons: a cure rate above 65% would be very satisfactory compared to all alternative drugs evaluated so far against schistosomiasis, and an efficacy slightly lower than that of PZQ would be largely compensated by the positive clinical effect due to concomitant malaria suppression. Note that this is likely to be marginal in North Senegal where malaria transmission is low, but this "dual" effect could be a major added-value in many other co-endemic regions with higher malaria transmission

Sample size was calculated by simulation to obtain 80% power. The required sample size is 300 schoolchildren per arm. To account for a 20% loss to follow up, the total number of children to be recruited will be 726 (363 per arm). With the same sample size, superiority of repeated courses of AM to PZQ (cure rate of at least 85% after 3 courses) can also be demonstrated with a similar power (i.e. secondary endpoint).

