- Mefloquine on the other hand displays strong activity against both larval and adult stages of *Sm* in mice ^{34,35} and the combination of mefloquine and PZQ was superior to either drug used alone in a mice model ³⁵. Only two small underpowered trials have evaluated the activity of mefloquine monotherapy against human schistosomiasis. Mefloquine alone appears less active than PZQ but cure rates increase with repeated administration. In the first exploratory phase 2 study ³⁶, a single course of mefloquine 25 mg/kg administered to 19 Ivorian schoolchildren infected with *Sh* (including 8 with *Sm* coinfection) had a lower efficacy than PZQ (ERR: 75% and CR: 21% versus 97% and 88% respectively). In the second preliminary trial ³⁷, two courses of mefloquine 15 mg/kg administered at one-month interval as intermittent preventive treatment against malaria to 30 Gabonese pregnant women with *Sh* infection resulted in an ERR of 80% after one course and of 98% after the second course, with a "final" CR of 47% at 6-week post-second course.

The combination artesunate-mefloquine (AM) is one of the five artemisinin-based combination therapies (ACTs) currently recommended by the WHO for the treatment of uncomplicated *Plasmodium falciparum (Pf)* malaria. A three-day course of AM consistently reaches cure rate above 95%. AM is the first-line treatment against *Pf* malaria for more than 15 years in many Latin American and Asian countries. Recently, AM has been developed as fixed drug combination (FDC) by the Drugs for Neglected Diseases initiative (DNDi) and is now manufactured at low price by Cipla (India) under two different co-formulations (for children and adults) that were pre-qualified by WHO in 2012.

The use of AM as antischistosomal therapy has however hardly been evaluated so far and results are contradictory and inconclusive. In the exploratory trial previously mentioned ³⁶, the efficacy of AM was similar to that of PZQ (ERR of 96% and CR of 61%). In another small (n=20/arm) exploratory trial in Ivorian schoolchildren with *Sh* infection ³⁸, adding mefloquine or AM to PZQ increased the ERR from 90 to 96% but not the CR (surprisingly low at 30% in all three arms). However, the sample size was not adequate to properly assess possible superiority.

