8.3.3. Primary analysis

The primary hypothesis for non-inferior efficacy will be assessed by calculating the two-sided 95% confidence interval (CI) for the difference in proportions of cured subjects. The CI will be calculated using Wilson's score method.

Interpretation of the CI will be as follows:

- if the two-sided 95% CI for the difference in cure rates (AM schedule PZQ schedule) lies entirely above -10% then non-inferiority of the AM schedule is concluded;
- if the 95% CI for the difference in cure rates includes -10%, then non-inferiority cannot be established;
- if the 95% CI for the difference in cure rates lies entirely below -10%, then the AM regimen is clinically inferior to the standard regimen.

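### Section 4.3 leaves 290, not 300, children per arm after 20% loss, and its 80% power rests on an unstated AM cure rate of about 75% or higher

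*Protocol*

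**What the plan says.** Section 4.3 sizes the trial on parasitological cure after the first AM course. The hypothesis is framed as "at least a 65% cure rate with AM as compared to a 75% cure rate with PZQ", and the section calls 65% the clinically acceptable threshold for non-inferiority. Power is 80%, by simulation. "The required sample size is 300 schoolchildren per arm". Then: "To account for a 20% loss to follow up, the total number of children to be recruited will be 726 (363 per arm"). The synopsis repeats the 726, the 80% and the 20%, and section 4.1 repeats 726 and 363.

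Section 8.3.3 fixes the test by "calculating the two-sided 95% confidence interval (CI) for the difference in proportions of cured subjects". It adds: "The CI will be calculated using Wilson's score method". If the interval "lies entirely above -10% then non-inferiority of the AM schedule is concluded".

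Section 1.2 gives the hypothesis for one AM course only in words: at least similar to PZQ. Section 1.1.1 reports an exploratory trial in which mefloquine alone "had a lower efficacy than PZQ (ERR: 75% and CR: 21% versus 97% and 88% respectively"). Of AM in that same trial it says "the efficacy of AM was similar to that of PZQ (ERR of 96% and CR of 61"). It describes the evidence on AM overall as contradictory and inconclusive.

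**The concern.** Two things in 4.3 call for a check. First, the evaluable number, the loss allowance and the recruitment target should agree, and they do not.

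Second, the power of a non-inferiority trial depends on the true rate assumed for the new treatment. The margin does not supply that rate. For the first course 4.3 prints one AM figure, 65%, and that is the margin restated (75% minus 10 points). For the secondary superiority claim, by contrast, the section does name the AM rate that it relies on (85% after three courses). For the primary claim, an ethics committee, data monitoring board or later reader cannot tell from 4.3 what must be true for the 80% to apply. Power is steep in that rate: a few points below PZQ turns a well-powered trial into a coin toss.

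**Working it through.** **Inputs.** PZQ cure rate 75% (4.3). Margin 10 percentage points and two-sided 95% interval, so one-sided 2.5% (8.3.3). Power 80%, 300 evaluable per arm, 363 recruited per arm, 20% loss (4.3). The assumed true AM rate is not given.

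**Step 1: reproduce the 300.** Take AM = PZQ = 75%. The usual unpooled formula gives

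n = 2 × 0.75 × 0.25 × (1.96 + 0.8416)² / 0.10² = 294.3, so 295 per arm.

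At 300 per arm, power is 80.7% by this formula. Section 8.3.3 names Wilson's score method. Taking this as the Newcombe–Wilson interval for a difference and enumerating all outcomes exactly gives 81.1%. So 300 and 80% belong together if AM equals PZQ at 75%.

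**Step 2: the loss allowance.**
- 363 × (1 − 0.20) = 290.4, so about 290 per arm remain.
- 300 / (1 − 0.20) = 375 per arm, 750 in total.
- 1 − 300/363 = 17.4%, the loss at which 363 still leaves 300.

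**Step 3: what the 10 missing children per arm cost.** At AM = PZQ = 75% and 290 per arm, power is 79.8%. That is 81.1 − 79.8 = 1.3 points lower, and still about 80%.

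**Step 4: power against the true AM rate.** PZQ 75%, margin 10 points, exact Newcombe–Wilson enumeration:

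| True AM cure rate | 290 per arm | 300 per arm |
|---|---|---|
| 75% | 79.8% | 81.1% |
| 74% | 70.5% | 72.0% |
| 72% | 48.6% | 49.9% |
| 70% | 27.6% | 28.4% |
| 65% | 2.6% | 2.6% |
| 61% | 0.1% | 0.1% |

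Above 75% power rises: at 290 per arm it is about 87% at 76% and 96% at 78%. The condition for 80% is therefore an AM rate of about 75% or higher. The value at 65% is the false-positive rate, as it must be at the margin.

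**Step 5: the cited evidence.** In the exploratory trial, egg reduction was 96% (AM) against 97% (PZQ), and these are close. Cure was 61% against 88%, a gap of 27 points, and cure is the primary endpoint here. The size of the AM arm is not given. If it was 18 to 30 children (an assumption; the mefloquine arm had 19), the Wilson 95% interval around 61% runs from about 39–43% up to about 76–80%, which includes 75%.

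**The case against.** The strongest reply is that nothing material is wrong. The trial as sized has 79.8% power against a stated 80%. Section 4.3 labels 65% as a threshold, 8.3.3 gives the matching margin, and section 1.2 hypothesises efficacy at least similar to PZQ, so equal rates can be inferred. Power at the margin equals the false-positive rate in every non-inferiority trial. Details of the simulation can sit elsewhere.

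Much of this stands. The loss slip is an inconsistency of labelling with almost no effect on power. It does not show that the trial is too small. But a protocol that prints a power should print the rate on which that power rests, and a hypothesis in words does not do that job when a 3-point shortfall takes power from 80% to 49%.

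Some stronger readings are tempting and do not hold:
- A reader might infer that loss was added by multiplying by about 1.2. The protocol gives no method, and 300 × 1.2 = 360, not 363. Since 290 / 0.8 = 362.5, a simulated result near 290 printed as a round 300 fits better, though that too is inference.
- A reader might infer that the power holds at 75% and nowhere else. Higher AM rates give more.
- A reader might infer that the protocol's own data contradict 75%. One exploratory figure of unknown precision, which the protocol calls inconclusive, cannot do that. It fails to support 75%, and no more can be said.
- A reader might infer that 65% is the assumed true AM rate. The text calls it a threshold.

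**Conclusion.** The point holds in two parts of unequal weight. The minor part: 300, 363 and 20% cannot all be right, because 363 per arm leaves 290 after 20% loss and keeps 300 only up to about 17% loss. The cost is about 1.3 points of power.

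The main part: the 80% is conditional on a true AM cure rate of about 75% or higher, which 4.3 does not state and which the one cited AM cure rate (61%, against 88% for PZQ) does not support.

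The figures assume PZQ at 75%, the Newcombe–Wilson form of the interval, and 290 children per arm in the primary per-protocol set. Exclusions from that set beyond 20% would lower them. A wording correction should be made. The calculation gives no reason to change enrolment.

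**What to change.** 1. In 4.3 and the synopsis, say that 363 per arm leaves about 290 after 20% loss (or 300 after 17% loss).
2. In the same places, state the basis of the power: about 80% if AM and PZQ both cure 75%, with a margin of −10 points and one-sided 2.5%.
3. Add that at 290 per arm power falls to about 49% if AM cures 72% and about 28% if it cures 70%.
4. In 1.1.1, limit the claim of similarity to egg reduction (96% against 97%) and report cure as 61% against 88%.

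The cost is wording only. Enrolment stays at 726, and the stated power becomes visibly conditional.
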